2.2 Secondary Objectives

Main Trial (ages 50-75)

Other objectives of this study are to assess implementation determinants and outcomes to inform plans for sustaining and scaling the CRC screening program. Our aims are to:

Aim 2: Assess the logistical feasibility and patient and provider acceptability of the mailed FIT outreach program (Arm 2), and

Aim 3: Estimate the cost and cost-effectiveness per person screened in each arm, as well as the level of resource investment required to scale-up the program statewide.

Sub-study (ages 45-49)

A new, secondary objective of this trial is to assess screening completion of a mailed FIT outreach program in patients aged 45-49 who are patients at the clinic.

We will:

1. Compare the proportion of patients who are current with any CRC screening prior to mailed FIT outreach and within 60 days of FIT mailing per electronic health record (EHR) query
2. Compare the proportion of patients who complete FIT within 60 days of the mailed FIT date, by experimental and active comparator arms
3. Describe the demographic characteristics of patients who complete FIT including, but not limited to, patient race, ethnicity, sex, and insurance status.

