3.1 Inclusion Criteria

Individuals must meet all of the following inclusion criteria to participate in this study:

- 3.1.1 Main trial: Age 50-75 years; Sub-study: Age 45-49 years
- 3.1.2 At average risk for CRC (“average risk” is defined as those patients who do not have any of the following: history of CRC, colonic adenomas, family history of CRC, or diagnosis of inflammatory bowel disease)
- 3.1.3 No record of fecal occult blood test (FOBT)/FIT within the past 12 months or colonoscopy within 10 years, sigmoidoscopy within 5 years, barium enema within 5 years, or computed tomography (CT) colonography within 10 years of the EHR query date
- 3.1.4 No record of any CRC diagnosis or total colectomy
- 3.1.5 Active patient (seen within the past 18 months) of RCCHC or BRH

Patients invited to participate in an interview will meet three additional inclusion criteria: aged 50-75; be assigned to study Arm 2 in the Main Trial; and have a positive (abnormal) FIT result as a participant in the screening program. We will not interview participants who are aged 45-49.

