4.3 Study Details

4.3.1 Cohort Ascertainment

Our study team will work with RCCHC and BRH to identify the population of patients at each site who meet study inclusion criteria (see section 3.1), using an automated query of the EHR at each site. Per protocols from two similar projects, all patients meeting inclusion criteria will be initially included in the study cohort. Because EHR records are based on best available information and may not reflect screenings performed at another facility, our study materials will include a phone number for patients to contact the study team to self-identify as ineligible. We will select patients for inclusion randomly from the cohort and replace as needed to reach the goal of up to 4,000 Main Trial participants from RCCHC and BRH and an additional 450 sub-study participants from RCCHC. Each FQHC will query their own EHR to identify patients who meet eligibility criteria. Designated staff at each FQHC will securely transfer the queried patient information from their EHR to a folder accessible only to IRB-approved study team members on a secure UNC server (UNC Teams folder designated specifically for each FQHC). The data set will contain, but not necessarily be limited to, patient name, age, sex, race/ethnicity, email address, mailing address, primary care provider, and the date of the most recent visit with one of the FQHC's primary care providers. Only authorized clinic and UNC project team representatives will be able to upload or remove data to UNC Teams. Each FQHC site will have its own folder, which will prevent access to data of patients not seen at their clinic. A member of the UNC project team will then transfer the patient data from UNC Teams to a REDCap database accessible only to UNC project team members.

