4.3.6 Data Collection

REDCap database: RCCHC and BRH will securely transfer patient information from the EHR to a secure SharePoint folder at UNC. A UNC research assistant will then upload the data to a REDCap database (developed based on two previous completed or ongoing studies). Data will include, but not necessarily be limited to, patient name, age, sex, race/ethnicity, mailing address, identified primary care provider, and if possible, the number of visits within the past 18 months with that provider. The study team has fully executed data use agreements in place with each FQHC. Designated approved members of the research team members will use the REDCap database to document whether patients were mailed a FIT kit and to track the status of FIT kit completion (yes or no), test result (positive or negative), contact with patients who have positive results (yes or no), and receipt of navigation support for colonoscopy (yes or no), including referrals for no-cost follow-up colonoscopy (yes or no) and transportation services (yes or no). Approved members of the UNC research team will also document in the REDCap database whether patients call to report they are ineligible for FIT screening per their screening and relevant medical history (e.g., already completed CRC screening elsewhere, have a medical history that places them at higher than average risk for CRC).

EHR: Each CHC will specify, train, and credential members of the UNC research team to conduct a manual review of participant EHRs 6 months or more after randomization to determine whether patients completed any CRC screening test (FIT, colonoscopy, flexible sigmoidoscopy, Cologuard) and, if so, the test result. As mentioned in the preceding paragraph, these data will be entered directly into the REDCap database by IRB-approved UNC staff members for analysis.

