7.2 Sample Size and Accrual

Main Trial

Our project funding supports a sample size of up to 4,000 patients at two clinical sites who are eligible for CRC screening. Using a 1:1 randomization approach, up to 2,000 RCCHC patients and up to 2,000 BRH patients will be randomized to the two study arms. For each FQHC, up to 1,000 patients will be randomized to each of the two arms. Our statistician performed formal power calculations for our primary study outcome comparing CRC screening completion for the intervention arm vs. the control arm, stratified by patient insurance status (4 strata: Medicare, Medicaid, commercial/private, and self-pay/other). Based on previous research, we anticipate that 25% of those receiving the intervention will complete CRC screening, and 17% of patients in the usual care arm will complete screening (8% difference between arms). We need 492 participants per arm, per strata to have at least 80% power to detect an 8% difference between study arms at 1-sided alpha level 0.0125 (3,936 participants total, which can be rounded up to 4,000). We calculated power by SAS PROC Power (SAS Institute, Cary, NC).

Sub-study (ages 45-49)

Sample size in this additional substudy is determined by feasibility and resource constraints. We have the resources to do intervention testing in this new age group (45-49) in a single clinic site. We will identify the cohort of participants who are eligible for screening on a given index date. We estimate 500 patients are in this age group and eligible for screening. We estimate that approximately 10%, i.e., 50 individual patients, will be current with screening at baseline. We will conduct the mailed intervention on the approximately 450 patients who are not current and then assess the screening rate at 60 days in same cohort. For outcome 2, we will use a 1:1 randomization approach to randomize patients the patients who are not current with screening to the two experimental study arms (envelope type).

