Our statistician performed formal power calculations for our study outcomes of change in CRC screening rate (pre-post) for this age group, as well as FIT return compared across the two arms. **Outcome 1:** We will observe baseline and post-intervention status of CRC for subjects who are not screened at baseline. For those who screened at baseline, we will not observe post-intervention CRC status, but we assume a high post-intervention screen rate for such subjects if they receive intervention before they receive screening. This leads to a paired binary data problem, and we test if the conversion rate (from not screened to screened) is high enough. A sample size of 500 achieves 80% power to detect an odds ratio of 2.922 using a two-sided McNemar test with a significance level of 0.05. This calculation is based on a difference between two paired proportions of 0.034 (P10-P01), where P10 (about 0.052) refers to the proportion of subjects who not screen at baseline but screen after intervention and the proportion (P01) of screen at baseline but not screen after intervention. This is an assumed number because we are not able to observe it but assume it's a very small number) is 0.018. The proportion of discordant pairs is 0.07. We will report baseline screening rate and post-intervention screening rate. **Outcome 2:** With 225 patients per arm, we reach 80% power, with 1-sided alpha 0.05, to detect a difference between the group FIT mail back rates of 0.102. The FIT mail back rate in Group 1 (the treatment group) is assumed to be 0.20 under the null hypothesis and 0.302 under the alternative hypothesis. The rate in Group 2 (the control group) is 0.20. We calculated power using SAS PROC Power (SAS Institute, Cary, NC).

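### Sub-study Outcome 1 compares screening status without requiring the qualifying test to be dated after mailing, so an earlier test entered late in the EHR would count as a conversion

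*Combined protocol and SAP*

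**What the plan says.** Section 2.2, sub-study item 1, sets Outcome 1: "Compare the proportion of patients who are current with any CRC screening prior to mailed FIT outreach and within 60 days of FIT mailing". The item adds that status is obtained by EHR query. Item 2, directly below, is worded differently: "Compare the proportion of patients who complete FIT within 60 days of the mailed FIT date". There the test itself is tied to the mailing; in item 1 it is the status that is tied to it.

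Section 7.2 says the team will mail the roughly 450 patients who are not current and "then assess the screening rate at 60 days in same cohort". For the test it says "we test if the conversion rate (from not screened to screened) is high enough". It describes P10 as "the proportion of subjects who not screen at baseline but screen after intervention". Section 7.3.4 names a test for Outcome 1 but adds no endpoint definition.

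The threshold for not being current is in section 3.1.3: "No record of fecal occult blood test (FOBT)/FIT within the past 12 months or colonoscopy within 10 years", with 5 years for sigmoidoscopy and barium enema and 10 years for CT colonography. Section 4.3.1 gives the reason for the call-in number: "Because EHR records are based on best available information and may not reflect screenings performed at another facility". Section 4.3.6 has staff "conduct a manual review of participant EHRs 6 months or more after randomization to determine whether patients completed any CRC screening test" and, if so, the result. It does not list the test date as an item to collect.

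**The concern.** Entry and response use the same threshold on the same record. A patient whose outside colonoscopy from four years ago was missing at the baseline query is not current then. If the report reaches the EHR before the follow-up query, the patient is current, and the status rule counts a conversion although no test followed the mailing.

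The error runs one way. Every mailed patient is not current by selection, and section 7.2 says the patients already screened at baseline will not be observed afterwards. Correcting the record can therefore only raise the post-mailing rate. Both envelope arms receive the mailing, so Outcome 1 has no unmailed group from which background record correction could be subtracted. The reported rise would mix response to outreach with better documentation.

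**Working it through.** **Inputs from section 7.2:** cohort 500, of whom about 50 are current at baseline and about 450 are mailed; P10 about 0.052; P01 0.018, assumed and not observable; discordant proportion 0.07; odds ratio 2.922; two-sided McNemar test at 0.05; 80% power.

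**Input not in the documents:** the fraction m of the 450 who have an earlier qualifying test that first appears in the EHR between the two queries. I use 0.5% to 5% as an assumed range.

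**1. The plan's own figure.** P10 = 0.07 × 2.922/3.922 = 0.0522 and P01 = 0.07/3.922 = 0.0178. Taking the discordant count as Binomial(500, 0.07) and applying an exact two-sided McNemar test within each count gives 80.0% power. The stated 80% reproduces.

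**2. Planned counts.** Conversions: 0.052 × 500 = 26. Assumed reverse changes: 0.018 × 500 = 9.

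**3. False conversions with no effect of mailing.** The expected count is 450m.
- m = 1%: 4.5, which is 17% of the planned 26 and 4.5/500 = 0.9 points of the cohort rate.
- m = 2%: 9, which is 35% of the planned 26 and 9/500 = 1.8 points.

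The planned net difference is 3.4 points.

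**4. What m implies about the query.** If 50 patients are recorded as current and every missed test surfaces, m = 1% means the query captured 50/54.5 = 92% of truly current patients, and m = 2% means 50/59 = 85%.

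**5. Conversions needed for significance (exact two-sided McNemar).**
- Reverse cell 0, as the data will be observed: 5 v 0 gives p = 2 × 0.5^5 = 0.063; 6 v 0 gives p = 2 × 0.5^6 = 0.031. Six is 1.3% of 450.
- Reverse cell filled with the assumed 9: 20 v 9 gives p = 0.061; 21 v 9 gives p = 0.043. Twenty-one is 4.7% of 450.

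**6. Probability that late-found records alone reach those counts, conversions ~ Binomial(450, m).**

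| m | 6 or more (reverse cell 0) | 21 or more (reverse cell 9) |
|---|---|---|
| 0.5% | 3% | about 0% |
| 1% | 30% | about 0% |
| 2% | 89% | less than 0.1% |
| 3% | 99% | 3% |
| 5% | over 99% | 66% |

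**7. A different null model.** Suppose genuine changes occur equally in both directions at 0.018, late-found records come on top, and the uncorrected McNemar test is used. The chance of a significant rise is then 2.5% at m = 0, 16% at 1% and 42% at 2%.

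Steps 6 and 7 show that the effect on the test depends heavily on how the reverse cell is treated. The inflation in step 3 does not.

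**The case against.** A reader might infer that the plan intends old tests to count as response. It does not say so. The description of P10 in section 7.2 points to screening after the intervention. That is probably the intent, but it glosses a power input; the endpoint in section 2.2 remains a status, and a query run as written would not separate the two.

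A reader might also infer that the call-in line or the hand chart review carries old tests into Outcome 1. The documents do not establish either. Calls are logged in REDCap as reports of ineligibility, with no stated link to the EHR. The chart review takes place 6 months or more after randomization and is not tied to the 60-day outcome, which item 1 says comes from an EHR query. Rereading the same EHR also cannot recover a test that was never entered in it. These are possible routes only. The mechanism that follows from the text is narrower: an outside result entered in the EHR between the two queries.

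The size is open to challenge too. No miss rate is given, and high values look unlikely: m = 10% would mean 45 hidden screened patients beside the 50 expected to be current, in a newly eligible, average-risk age group. With an empty reverse cell, any 6 conversions reject, including genuine ones, so the 30% and 89% figures partly reflect the unobservable cell and the missing control. They also assume the McNemar test of section 7.2, whereas section 7.3.4 names a Mantel-Haenszel test; that is a separate matter. All of this stands, and it limits the claim to a definition that permits upward bias of unknown size.

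**Conclusion.** The point holds as a defect in the endpoint definition. As written, Outcome 1 would count an earlier test entered after the baseline query as a conversion; the error can only inflate the rise, and the design offers no comparison to remove it. At an assumed 1-2% of the 450, it would add about 5 to 9 conversions, or 0.9 to 1.8 points, against 26 planned. Whether that alone would give a significant result depends on the reverse cell: 6 conversions suffice if it is empty, and 21 are needed if it holds the assumed 9. These are illustrations, not estimates of the bias to expect. The outcome is a secondary, uncontrolled, single-clinic comparison. The envelope comparison (Outcome 2) is already tied to a FIT completed within 60 days of mailing and, like the main trial, lies outside this point.

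**What to change.** In section 2.2 item 1 and section 7.2 Outcome 1, define a conversion as a qualifying test with a date of service after the FIT mailing date and no later than day 60. Add the test date to the items collected. If a qualifying test dated before mailing comes to light by any route, recode that patient as current at baseline in both the before and the after rate, and report how many were recoded. The introductory letter goes out about two weeks before the kit (section 4.3.3), so state explicitly that tests dated between the two fall on the baseline side.

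The cost is a few lines of protocol text, slightly more data handling, and possibly a smaller reported rise. No stated sample size changes.

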3.0 PATIENT ELIGIBILITY

We will use the inclusion and exclusion criteria below to guide our electronic health record (EHR) query to identify eligible patients for the main trial and added cohort of patients ages 45-49.

3.1 Inclusion Criteria

Individuals must meet all of the following inclusion criteria to participate in this study:

- 3.1.1 Main trial: Age 50-75 years; Sub-study: Age 45-49 years
- 3.1.2 At average risk for CRC (“average risk” is defined as those patients who do not have any of the following: history of CRC, colonic adenomas, family history of CRC, or diagnosis of inflammatory bowel disease)
- 3.1.3 No record of fecal occult blood test (FOBT)/FIT within the past 12 months or colonoscopy within 10 years, sigmoidoscopy within 5 years, barium enema within 5 years, or computed tomography (CT) colonography within 10 years of the EHR query date
- 3.1.4 No record of any CRC diagnosis or total colectomy
- 3.1.5 Active patient (seen within the past 18 months) of RCCHC or BRH

Patients invited to participate in an interview will meet three additional inclusion criteria: aged 50-75; be assigned to study Arm 2 in the Main Trial; and have a positive (abnormal) FIT result as a participant in the screening program. We will not interview participants who are aged 45-49.

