3.2 Exclusion Criteria

[figure not shown]
All individuals meeting any of the exclusion criteria at baseline will be excluded from study participation:

- 3.2.1** Main trial: Age younger than 50 years or older than 75 years; Sub-study: Age younger than 45 years or older than 49 years
- 3.2.2** Not at average risk for CRC (“average risk” is defined as those patients who do not have any of the following: history of CRC, colonic adenomas, family history of CRC, or diagnosis of inflammatory bowel disease)
- 3.2.3** Record of FOBT/FIT within the past 12 months or colonoscopy within 10 years, sigmoidoscopy within 5 years; barium enema within 5 years, or CT colonography within 10 years of the EHR query date
- 3.2.4** Record of any CRC diagnosis or total colectomy
- 3.2.5** Not an active patient (not seen within the past 18 months) of RCCHC or BRH

Patients will not be invited to participate in an interview if they meet additional exclusion criteria: be assigned to study Arm 1, do not return a FIT as a participant in the screening program, or have a negative (normal) FIT result as a participant in the screening program.

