4.0 STUDY PLAN

4.1 Main Trial Schema

This trial will enroll up to 4,000 patients aged 50-75 years who are not up-to-date with CRC screening. The primary purpose of this study is to assess the effectiveness of mailed FIT outreach on CRC screening completion in a community health center context in both northeastern and western North Carolina, by comparing the proportion of patients screened across two study arms.

All participants assigned to Arm 2 will be eligible to receive two intervention rounds, scheduled about 54 weeks apart. These two intervention rounds will allow us to longitudinally assess adherence to the United States Preventive Services Task Force recommendations for annual screening with FIT (see 1.2). Arm assignment will remain the same across both intervention rounds. Patients will be

included in the second intervention round if they continue to meet the study's IRB-approved inclusion criteria for age, risk, screening history, CRC or colectomy history, and active patient status (seen within the past 18 months). In accordance with clinical recommendations, patients who receive a positive (abnormal) FIT result in the first round will not be included in the second round of FIT mailings (they will not be mailed a FIT).

We anticipate that the approximate time for the study team to complete each of the two rounds of study mailings will be 3 months, and patients' active participation during each round will last from 4 weeks (for patients with a FIT negative result and needed few, if any, reminders to complete the FIT) up to 6 months (for patients with a positive FIT result who need a follow-up colonoscopy, and needed several reminders to complete the FIT). For each round, we will assume that patients who have not completed screening (FIT, screening colonoscopy, or follow-up colonoscopy) after 6 months following the FIT kit mailing, do not intend to do so. We will randomly select an equal number of control group participants to correspond to each mailing wave for intervention participants, and will track both intervention and control participants for the same time period (from Introductory Letter mailing to 6-months post-mailing).

[figure not shown]

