4.3.5 Notification of Results and Follow-up on Positive FITs

Negative FIT result: BRH patients with a negative FIT result, per BRH current clinical protocol, will receive a letter from their primary care provider. For RCCHC patients with a negative FIT result, IRB-approved UNC research staff will send patients a letter (approved by RCCHC) to notify them of the negative result. The letter will include a reminder that the test should be repeated in 12 months.

Positive FIT result: For patients with a positive (abnormal) FIT result, the patient's primary care provider or the provider's designee will call the patient, per current standard protocol at each FQHC. The primary care provider or primary care provider's designee will inform the patient of the positive result and need for a follow-up colonoscopy. After a patient is notified of a positive result, the patient navigator (employed by UNC and credentialed by each FQHC) will call the patient to offer information and support, including navigation services to access colonoscopy. Navigation services include, but are not necessarily limited to, referral and assistance with registering for charity care programs operating in each region (Hertford Health Access program for RCCHC and Digestive Health Partners-Hendersonville or Pardee Hospital Charity Care program for BRH) including no-cost colonoscopy (for uninsured patients) and, if available, transportation services to and from the colonoscopy appointment (for all patients). Patients who do not qualify for charity care may receive no-cost colonoscopy, supported using study funding and/or donated colonoscopy services. The patient navigator will help navigate the patient to these services, if needed.

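### Eligibility checks the date of an earlier stool test but not its result, so a patient with an old, unresolved positive can be mailed a repeat FIT

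*Combined protocol and SAP*

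**What the plan says.** Criterion 3.1.3 requires "No record of fecal occult blood test (FOBT)/FIT within the past 12 months or colonoscopy within 10 years", with date windows for three other examinations. Criterion 3.2.3 excludes the reverse: "Record of FOBT/FIT within the past 12 months or colonoscopy within 10 years, sigmoidoscopy within 5 years", and so on. Both are tied to the EHR query date. The average-risk definition (3.1.2, 3.2.2) lists colorectal cancer, adenomas, family history and inflammatory bowel disease. Criteria 3.1.4 and 3.2.4 cover a cancer diagnosis or total colectomy. Section 3.0 uses the same criteria for the main trial and the sub-study.

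Section 4.1 has the one rule based on a result. Citing clinical recommendations, it says that "patients who receive a positive (abnormal) FIT result in the first round will not be included in the second round of FIT mailings". Otherwise round 2 takes patients who still meet the "IRB-approved inclusion criteria for age, risk, screening history, CRC or colectomy history, and active patient status".

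Section 4.3.5 states what a positive means: the primary care provider or designee is to "inform the patient of the positive result and need for a follow-up colonoscopy". For a negative FIT, RCCHC patients get a letter sent by study staff: "The letter will include a reminder that the test should be repeated in 12 months". BRH patients get a letter from their primary care provider.

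The other check is self-report. In 4.3.1, "our study materials will include a phone number for patients to contact the study team to self-identify as ineligible". Section 4.3.6 gives as examples of ineligibility: "already completed CRC screening elsewhere, have a medical history that places them at higher than average risk for CRC".

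**The concern.** A positive stool test with no completed work-up leaves a patient needing a diagnostic examination. Another screening test does not meet that need. Sections 4.1 and 4.3.5 both accept this for positives found in the trial. At baseline the only stool-test question is whether one was done in the past year, so a positive from, say, 18 months ago is treated like a negative from 18 months ago.

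What is at stake is false reassurance. It arises only for an affected patient who returns the repeat kit and tests negative. At RCCHC that patient then receives a letter from study staff advising a repeat in 12 months, which is an action of the study itself. The mailing also runs under a requested consent waiver that rests on minimal risk (8.1).

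**Working it through.** **Does such a patient pass every criterion?** Take a patient of eligible age, seen in the past 18 months, whose FIT was positive 18 months before the query and who has no later examination on record.

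- 3.1.1 and 3.1.5 (age, active patient): met.
- 3.1.2 (average risk): met; an earlier positive stool test is not among the four conditions.
- 3.1.3 (dates): met; the FIT is older than 12 months and no listed examination falls in its window.
- 3.1.4 (cancer or colectomy): met.
- The round-1 rule in 4.1: does not apply, because the positive predates the trial.

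Section 4.3.1 puts everyone who meets the criteria into the initial cohort. Under 4.3.3, a kit follows in Arm 2 and in both sub-study arms.

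**How many?** The documents give no share with this history. The figures below convert an assumed 1%. Inputs from 7.2: 4,000 main-trial patients, 1:1; 450 sub-study patients; 25% planned completion in Arm 2; 20% to 30.2% planned sub-study return.

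- Main trial: 4,000 × 0.01 = 40, of whom 40 / 2 = 20 are in Arm 2.
- Arm 2 returns per round: 20 × 0.25 = 5; at an assumed 50% return, 20 × 0.50 = 10.
- Negative repeats, if 10% to 50% test positive again (assumed): 5 × 0.5 = 2.5 to 5 × 0.9 = 4.5; at 10 returns, 5 to 9.
- Sub-study: 450 × 0.01 = 4.5 mailed; 4.5 × 0.20 = 0.9 to 4.5 × 0.302 = 1.36 returned; 0.9 × 0.5 = 0.45 to 1.36 × 0.9 = 1.22 negative.

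The 25% is an average over all of Arm 2 and includes colonoscopy, which would make it too high for kit returns. But these patients have already completed a stool test once, which could make it too low. Two rounds are also planned. The counts are therefore not limits in either direction.

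**Effect on the arm comparison.** The history predates randomisation and is expected equally in both arms. If the arm difference in this group were 10 points away from everyone else's (assumed), a share of 0.5% to 2% would move the overall difference by 0.005 × 10 = 0.05 to 0.02 × 10 = 0.2 points, against the planned 8.

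**Cost in power.** First, the plan's own figure. For 25% versus 17%, one-sided alpha 0.0125 and 80% power, with pooled variance under the null:

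n = [2.2414 × √(2 × 0.21 × 0.79) + 0.8416 × √(0.25 × 0.75 + 0.17 × 0.83)]² / 0.08² = 491.5, so 492 per arm per stratum. Over 2 arms and 4 strata that is 3,936, as stated in 7.2.

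With equal strata (assumed), 4,000 patients give 500 per arm per stratum. Excluding 2% without replacement leaves 490.

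| Comparison | n per arm | Power |
|---|---|---|
| Main trial, per stratum | 500 | 80.7% |
| Main trial, per stratum | 492 | 80.0% |
| Main trial, per stratum | 490 | 79.9% |
| Sub-study, 30.2% vs 20%, one-sided 0.05 | 225 | 80.4% |
| Sub-study, 2% fewer | 220.5 | 79.7% |

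The loss is under one percentage point in each case.

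**The case against.** The strongest case on the other side has four parts.

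- **No enrolled patient is shown to have this history.** This stands. Every count above depends on an assumed share.
- **Net harm is not established.** Usual care has left these patients without a recorded work-up. A repeat positive would bring a provider call, navigation and perhaps a no-cost colonoscopy (4.3.5), and patients who do not return the kit are no worse off. This stands as a limit on the harm. It does not justify mailing the kit, because returning the names to the health centre offers a more direct route to follow-up.
- **Safeguards exist.** An introductory letter precedes the kit, patients can phone, the examples in 4.3.6 are not exhaustive, and the query specification and letters may say more than the protocol does. These are partial protections. The phone line is voluntary and needs the patient to see an old positive as a reason to call. Health-centre follow-up has, by definition, left no recorded work-up in these patients.
- **The protocol says nothing on how long a positive stays relevant.** This is true: 4.1 concerns rounds about 54 weeks apart. It bears on how far back to look, not on whether to ask.

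A reader might infer that the protocol contradicts itself. It does not: 4.1 covers positives found in the trial, and the baseline criteria are silent on earlier ones. A reader might also infer that the trial cancels a pending colonoscopy referral. Nothing in the documents says so.

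**Conclusion.** The gap is real as written: an old positive stool test without recorded follow-up passes every baseline criterion, and in Arm 2 or either sub-study arm a repeat FIT is mailed. It is a missing patient-safety safeguard that is cheap to add, and the change should be made.

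The number affected cannot be determined. Per assumed 1%, about 20 Arm 2 and 4 to 5 sub-study patients would be mailed a kit, with about 5 Arm 2 returns per round at 25% and about 10 at 50%. Sub-study exposure is probably small, because ages 45-49 became eligible for screening only in May 2021 (1.1).

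It would be tempting to go on to say that the primary comparison is compromised. The documents do not support that: both arms are drawn by the same criteria before randomisation, and the illustrative shift is at most 0.2 points against 8.

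**What to change.** **Criterion.** Add to 3.1.3, and mirror in 3.2.3: *no recorded positive FOBT/FIT without a later recorded colonoscopy or other completed diagnostic work-up*. Apply it in the EHR query before randomisation, in the main trial and the sub-study. Replace excluded candidates where the pool allows, as 4.3.1 permits, and return their names to the health centre for follow-up under its usual protocol.

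**Patients already randomised, and round 2.** Use the rule only to withhold a FIT mailing, never as an eligibility or analysis exclusion. Section 4.1 re-applies the screening-history criterion at round 2, so this needs to be stated. By then positives include results obtained after randomisation, and Arm 2 is expected to have more tests, so excluding on them would remove patients unequally. Analyse everyone in the assigned arm. If the health centre is notified, do so identically in both arms: controls are otherwise not contacted (4.3.7.1) and colonoscopy counts toward the primary outcome (2.1). Report this as a small departure from usual care.

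**Cost.**
- One sentence, plus the last stool-test result and date in the query. Results are entered in the EHR (4.3.4), but the protocol does not say that older ones can be queried; if not, a chart check is needed.
- Patients worked up elsewhere without a record would be excluded.
- Replacements: by the counts in 1.2, at most 3,100 − 2,000 = 1,100 spare at RCCHC and 2,600 − 2,000 = 600 at BRH. Fewer are likely, because 1.2 does not say that all criteria were applied. Without replacement, 4,000 − 3,936 = 64 exclusions (1.6%) fit within the planned margin if strata are equal. The sub-study enrols everyone eligible, so it loses one patient per exclusion.
- Withholding kits from 1% of Arm 2 while keeping those patients in the analysis dilutes the planned difference by about 0.01 × 8 = 0.08 points.
- Table 1 places both main-trial rounds in Years 1 to 3, and the sub-study text dates from Year 4 of the award (5.1). If main-trial mailings are complete, the change reaches mainly the sub-study.
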